11.1.1 Definitions

Evaluable for Target Disease response. Only those participants who have measurable disease present at baseline, have received at least one cycle of therapy, and have had their disease re-evaluated will be considered evaluable for target disease response. These participants will have their response classified according to the definitions stated below. (Note: Participants who exhibit objective disease progression prior to the end of cycle 1 will also be considered evaluable.)

Evaluable Non-Target Disease Response. Participants who have lesions present at baseline that are evaluable but do not meet the definitions of measurable disease, have received at least one cycle of therapy, and have had their disease re-evaluated will be considered evaluable for non-target disease. The response assessment is based on the presence, absence, or unequivocal progression of the lesions.

11.1.2 Disease Parameters

Measurable disease. Measurable lesions are defined as those that can be accurately measured in at least one dimension (longest diameter to be recorded) as ≥ 20 mm by chest x-ray or ≥ 10 mm with CT scan, MRI, or calipers by clinical exam. All tumor measurements must be recorded in millimeters (or decimal fractions of centimeters).

Note: Tumor lesions that are situated in a previously irradiated area will not be considered measurable.

Malignant lymph nodes. To be considered pathologically enlarged and measurable, a lymph node must be ≥ 15 mm in short axis when assessed by CT scan (CT scan slice thickness recommended to be no greater than 5 mm). At baseline and in follow-up, only the short axis will be measured and followed.

Non-measurable disease. All other lesions (or sites of disease), including small lesions (longest diameter <10 mm or pathological lymph nodes with ≥10 to <15 mm short axis), are considered non-measurable disease. Bone lesions, leptomeningeal disease, ascites, pleural/pericardial effusions, lymphangitis cutis/pulmonitis, inflammatory breast disease, abdominal masses (not followed by CT or MRI), and cystic lesions are all considered non-measurable

Note: Cystic lesions that meet the criteria for radiographically defined simple cysts should not be considered as malignant lesions (neither measurable nor non-measurable) since they are, by definition, simple cysts.

'Cystic lesions' thought to represent cystic metastases can be considered as measurable lesions, if they meet the definition of measurability described above. However, if non-cystic lesions are present in the same participant, these are preferred for selection as target lesions.

Target lesions. All measurable lesions up to a maximum of 2 lesions per organ and 5 lesions in total, representative of all involved organs, should be identified as **target lesions** and recorded and measured at baseline. Target lesions should be selected on the basis of their size (lesions with the longest diameter), be representative of all involved organs, but in addition should be those that lend themselves to reproducible repeated measurements. It may be the case that, on occasion, the largest lesion does not lend itself to reproducible measurement in which circumstance the next largest lesion which can be measured reproducibly should be selected. A sum of the diameters (longest for non-nodal lesions, short axis for nodal lesions) for all target lesions will be calculated and reported as the baseline sum diameters. If lymph nodes are to be included in the sum, then only the short axis is added into the sum. The baseline sum diameters will be used as reference to further characterize any objective tumor regression in the measurable dimension of the disease.

Non-target lesions. All other lesions (or sites of disease) including any measurable

lesions over and above the 5 target lesions should be identified as **non-target lesions** and should also be recorded at baseline. Measurements of these lesions are not required, but the presence, absence, or in rare cases unequivocal progression of each should be noted throughout follow up.

11.1.3 Methods for Evaluation of Disease

All measurements should be taken and recorded in metric notation using a ruler, calipers, or a digital measurement tool. All baseline evaluations should be performed as closely as possible to the beginning of treatment and never more than 4 weeks before the beginning of the treatment.

The same method of assessment and the same technique should be used to characterize each identified and reported lesion at baseline and during follow-up. Imaging-based evaluation is preferred to evaluation by clinical examination unless the lesion(s) being followed cannot be imaged but are assessable by clinical exam.

Clinical lesions. Clinical lesions will only be considered measurable when they are superficial (e.g., skin nodules and palpable lymph nodes) and ≥ 10 mm in diameter as assessed using calipers (e.g., skin nodules). In the case of skin lesions, documentation by color photography, including a ruler to estimate the size of the lesion, is recommended.

Chest x-ray. Lesions on chest x-ray are acceptable as measurable lesions when they are clearly defined and surrounded by aerated lung; however, CT is preferable.

Conventional CT and MRI. This guideline has defined measurability of lesions on CT scan based on the assumption that CT thickness is 5mm or less. If CT scans have slice thickness greater than 5 mm, the minimum size of a measurable lesion should be twice the slice thickness. MRI is also acceptable in certain situations (*e.g.* for body scans).

Use of MRI remains a complex issue. MRI has excellent contrast, spatial, and temporal resolution; however, there are many image acquisition variables involved in MRI, which greatly impact image quality, lesion conspicuity, and measurement. Furthermore, the availability of MRI is variable globally. As with CT, if an MRI is performed, the technical specifications of the scanning sequences used should be optimized for the evaluation of the type and site of disease. Furthermore, as with CT, the modality used at follow-up should be the same as was used at baseline and the lesions should be measured/assessed on the same pulse sequence. It is beyond the scope of the RECIST guidelines to prescribe specific MRI pulse sequence parameters for all scanners, body parts, and diseases. Ideally, the same type of scanner should be used and the image acquisition protocol should be followed as closely as possible to prior scans. Body scans should be performed with breath-hold scanning techniques, if possible.

FDG-PET. While FDG-PET response assessments need additional study, it is sometimes reasonable to incorporate the use of FDG-PET scanning to complement CT scanning in assessment of progression (particularly possible 'new' disease). New lesions on the basis

of FDG-PET imaging can be identified according to the following algorithm:

- (a) Negative FDG-PET at baseline, with a positive FDG-PET at follow-up is a sign of PD based on a new lesion.
- (b) No FDG-PET at baseline and a positive FDG-PET at follow-up: If the positive FDG-PET at follow-up corresponds to a new site of disease confirmed by CT, this is PD. If the positive FDG-PET at follow-up is not confirmed as a new site of disease on CT, additional follow-up CT scans are needed to determine if there is truly progression occurring at that site (if so, the date of PD will be the date of the initial abnormal FDG-PET scan). If the positive FDG-PET at follow-up corresponds to a pre-existing site of disease on CT that is not progressing on the basis of the anatomic images, this is not PD.
- (c) FDG-PET may be used to upgrade a response to a CR in a manner similar to a biopsy in cases where a residual radiographic abnormality is thought to represent fibrosis or scarring. The use of FDG-PET in this circumstance should be prospectively described in the protocol and supported by disease-specific medical literature for the indication. However, it must be acknowledged that both approaches may lead to false positive CR due to limitations of FDG-PET and biopsy resolution/sensitivity.

Note: A 'positive' FDG-PET scan lesion means one which is FDG avid with an uptake greater than twice that of the surrounding tissue on the attenuation corrected image.

PET-CT. At present, the low dose or attenuation correction CT portion of a combined PET-CT is not always of optimal diagnostic CT quality for use with RECIST measurements. However, if the site can document that the CT performed as part of a PET-CT is of identical diagnostic quality to a diagnostic CT (with IV and oral contrast), then the CT portion of the PET-CT can be used for RECIST measurements and can be used interchangeably with conventional CT in accurately measuring cancer lesions over time. Note, however, that the PET portion of the CT introduces additional data which may bias an investigator if it is not routinely or serially performed.

MIBG (meta-iodobenzylguanidine). The following is recommended, to assure high quality images are obtained.

Patient preparation: Iodides, usually SSKI (saturated solution of potassium iodide), are administered to reduce thyroidal accumulation of free radioiodine, preferably beginning the day prior to injection and continuing for 3 additional days (4 days total). For infants and children, one drop t.i.d. is sufficient, for adolescents 2 drops t.i.d., and for adults 3 drops t.i.d. Participants and/or parents are asked about exposure to potential interfering agents. If none is noted, an indwelling intravenous line is established. The dose of MIBG is administered by slow intravenous injection over 90 seconds.

Images from the head to the distal lower extremities should be obtained.

I-123MIBG scintigraphy is performed to obtain both planar and tomographic images.

Planar: Anterior and posterior views from the top of the head to the proximal lower extremities are obtained for 10 minutes at 24 hours and occasionally at 48 hours following injection of 10 mCi/1.7 square meters of body surface area (\sim 150 μ Ci/kg, maximum 10 mCi). Anterior views of the distal lower extremities are adequate. A large field of view dual head gamma camera with low energy collimators is preferred.

SPECT: Most participants receiving I-123 MIBG also undergo SPECT at 24 hours, using a single or multi-headed camera with a low energy collimator. The camera is rotated through 360 degrees, 120 projections at 25 seconds per stop. Data are reconstructed using filtered back projections with a Butterworth filter and a cut off frequency of 0.2-0.5. SPECT/CT may be performed at institutions with this capacity.

Ultrasound. Ultrasound is not useful in assessment of lesion size and should not be used as a method of measurement. Ultrasound examinations cannot be reproduced in their entirety for independent review at a later data and, because they are operator dependent, it cannot be guaranteed that the same technique and measurements will be taken from one assessment to the next. If new lesions are identified by ultrasound in the course of the study, confirmation by CT or MRI is advised. If there is concern about radiation exposure from CT, MRI may be used instead of CT in selected instances.

Endoscopy, Laparoscopy. The utilization of these techniques for objective tumor evaluation is not advised. However, such techniques may be useful to confirm complete pathological response when biopsies are obtained or to determine relapse in trials where recurrence following complete response (CR) or surgical resection is an endpoint.

Tumor markers. Tumor markers alone cannot be used to assess response. If markers are initially above the upper normal limit, they must normalize for a participant to be considered in complete clinical response. Specific guidelines for both CA-125 response (in recurrent ovarian cancer) and PSA response (in recurrent prostate cancer) have been published [*JNCI* 96:487-488, 2004; *J Clin Oncol* 17, 3461-3467, 1999; *J Clin Oncol* 26:1148-1159, 2008]. In addition, the Gynecologic Cancer Intergroup has developed CA-125 progression criteria which are to be integrated with objective tumor assessment for use in first-line trials in ovarian cancer [*JNCI* 92:1534-1535, 2000].

Cytology, Histology. These techniques can be used to differentiate between partial responses (PR) and complete responses (CR) in rare cases (*e.g.*, residual lesions in tumor types, such as germ cell tumors, where known residual benign tumors can remain).

The cytological confirmation of the neoplastic origin of any effusion that appears or worsens during treatment when the measurable tumor has met criteria for response or stable disease is mandatory to differentiate between response or stable disease (an effusion may be a side effect of the treatment) and progressive disease.

11.1.3.1 Evaluation of Target Lesions

Complete Response (CR): Disappearance of all target lesions. Any pathological lymph nodes (whether target or non-target) must have reduction in short axis to <10 mm.

Partial Response (PR): At least a 30% decrease in the sum of the diameters of target lesions, taking as reference the baseline sum diameters.

Progressive Disease (PD): At least a 20% increase in the sum of the diameters of target lesions, taking as reference the smallest sum on study (this includes the baseline sum if that is the smallest on study). In addition to the relative increase of 20%, the sum must also demonstrate an absolute increase of at least 5 mm. (Note: the appearance of one or more new lesions is also considered progressions).

Stable Disease (SD): Neither sufficient shrinkage to qualify for PR nor sufficient increase to qualify for PD, taking as reference the smallest sum diameters while on study.

11.1.3.2 Evaluation of Non-Target Lesions

Complete Response (CR): Disappearance of all non-target lesions and normalization of tumor marker level. All lymph nodes must be non-pathological in size (<10 mm short axis).

Note: If tumor markers are initially above the upper normal limit, they must normalize for a patient to be considered in complete clinical response.

Non-CR/Non-PD: Persistence of one or more non-target lesion(s) and/or maintenance of tumor marker level above the normal limits.

Progressive Disease (PD): Appearance of one or more new lesions and/or *unequivocal progression* of existing non-target lesions. *Unequivocal progression* should not normally trump target lesion status. It must be representative of overall disease status change, not a single lesion increase.

Although a clear progression of "non-target" lesions only is exceptional, the opinion of the treating physician should prevail in such circumstances, and the progression status should be confirmed at a later time by the review panel (or Principal Investigator).

11.1.3.3 Evaluation of New Lesions

The finding of a new lesion should be unequivocal (i.e. not due to difference in scanning technique, imaging modality, or findings thought to represent something other than tumor (for example, some 'new' bone lesions may be simply healing or flare of pre-existing lesions). However, a lesion identified on a follow-up scan in an

anatomical location that was not scanned at baseline is considered new and will indicate PD. If a new lesion is equivocal (because of small size etc.), follow-up evaluation will clarify if it truly represents new disease and if PD is confirmed, progression should be declared using the date of the initial scan on which the lesion was discovered.

Duration of overall response: The duration of overall response is measured from the time measurement criteria are met for CR or PR (whichever is first recorded) until the first date that recurrent or progressive disease is objectively documented (taking as reference for progressive disease the smallest measurements recorded since the treatment started, or death due to any cause. Participants without events reported are censored at the last disease evaluation).

Duration of overall complete response: The duration of overall CR is measured from the time measurement criteria are first met for CR until the first date that progressive disease is objectively documented, or death due to any cause. Participants without events reported are censored at the last disease evaluation.

Duration of stable disease: Stable disease is measured from the start of the treatment until the criteria for progression are met, taking as reference the smallest measurements recorded since the treatment started, including the baseline measurements.

11.1.5 Progression-Free Survival

Overall Survival: Overall Survival (OS) is defined as the time from randomization (or registration) to death due to any cause, or censored at date last known alive.

Progression-Free Survival: Progression-Free Survival (PFS) is defined as the time from randomization (or registration) to the earlier of progression or death due to any cause. Participants alive without disease progression are censored at date of last disease evaluation.

Time to Progression: Time to Progression (TTP) is defined as the time from randomization (or registration) to progression, or censored at date of last disease evaluation for those without progression reported.

11.1.6 Response Review

Evaluation of scans will be done centrally at the DFCI using the Tumor Metrics Core.

12. DATA REPORTING / REGULATORY REQUIREMENTS

Adverse event lists, guidelines, and instructions for AE reporting can be found in 7.1 (Adverse

Events: List and Reporting Requirements).

12.1 Data Reporting

12.1.1 Method

The ODQ will collect, manage, and perform quality checks on the data for this study.

12.1.2 Responsibility for Data Submission

Investigative sites within DF/HCC or DF/PCC are responsible for submitting data and/or data forms to the InForm application designed by CTRIO according to the schedule set by CTRIO.

12.2 Data Safety Monitoring

The DF/HCC Data and Safety Monitoring Committee (DSMC) will review and monitor toxicity and accrual data from this study. The committee is composed of clinical specialists with experience in oncology and who have no direct relationship with the study. Information that raises any questions about participant safety will be addressed with the Overall PI and study team.

The DSMC will review each protocol up to four times a year or more often if required to review toxicity and accrual data. Information to be provided to the committee may include: up-to-date participant accrual; current dose level information; DLT information; all grade 2 or higher unexpected adverse events that have been reported; summary of all deaths occurring within 30 days of intervention for Phase I or II protocols; for gene therapy protocols, summary of all deaths while being treated and during active follow-up; any response information; audit results, and a summary provided by the study team. Other information (e.g. scans, laboratory values) will be provided upon request.

13. STATISTICAL CONSIDERATIONS

A standard 3+3 design is planned for the dose finding phase I portion of the trial. The phase I portion of the trial will require a minimum of six and a maximum of 18 patients to determine the MTD and RP2D. Following identification of the MTD and RP2D, a single-arm phase II trial will commence. A total of 25 patients with metastatic melanoma harboring a *BRAF* V600E or V600K mutation will be enrolled to the phase II portion of the trial.

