5. TREATMENT PLAN

5.1 Treatment Regimen

The starting dose for the phase I portion of the trial will be dose level 1: LY3022855 50 mg IV weekly, vemurafenib 960 mg by mouth twice per day (BID), and cobimetinib 60 mg by mouth once daily on days 1-21 of the cycle. The dose escalation scheme is depicted in **Table 10**. One cycle is defined as 28 consecutive days. Treatment will be administered on an outpatient basis. Reported adverse events and potential risks are described in **Section** 7. Appropriate dose modifications are described in **6.3**. No investigational or commercial agents or therapies other than those described below may be administered with the intent to treat the participant's malignancy, with the exception of palliative radiation therapy or surgical resection to non-target lesions with prior permission from the principal investigator. Bisphosphonate use is permitted.

Table 10: Phase I Dose Escalation Schedule

Dose Level	Dose
------------	------

	LY3022855	Vemurafenib	Cobimetinib
1 (Starting Dose Level)	50 mg IV weekly	960 mg BID	60 mg daily (taken on days 1-21)
2	75 mg IV weekly	960 mg BID	60 mg daily (taken on days 1-21)
3	100 mg IV weekly	960 mg BID	60 mg daily (taken on days 1-21)

Three patients will be enrolled to dose level 1. The maximum dose of LY3022855 to be evaluated in the triplet combination will not exceed the recommended phase 2 flat dose of singeagent LY3022855. Enrollment to the dose level can occur in parallel with no observation period or delay between the start of therapy for each enrolled patient. The patients will be observed during the first cycle of therapy for toxicity consistent with a dose-limiting toxicity (DLT) definition, located in **5.4**.

Dose escalation will proceed in a standard 3+3 fashion according to the scheme in **Table 11**.

Table 11: Phase I Dose Escalation Decision Criteria

Number of Participants with DLT at a Given Dose Level	Escalation Decision Rule
0 out of 3	Enter 3 participants at the next dose level.
≥ 2	Dose escalation will be stopped. This dose level will be declared the maximally administered dose (highest dose administered). Three (3) additional participants will be entered at the next lowest dose level if only 3 participants were treated previously at that dose.

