1 out of 3	 Enter at least 3 more participants at this dose level. If 0 of these 3 participants experience DLT, proceed to the next dose level. If 1 or more of this group suffer DLT, then dose escalation is stopped, and this dose is declared the maximally administered dose. Three (3) additional participants will be entered at the next lowest dose level if only 3 participants were treated previously at that dose.
≤ 1 out of 6 at highest dose level below the maximally administered dose	This is generally the RP2D. At least 6 participants must be entered at the RP2D.

The maximally administered dose (MAD) of the study medications will be defined as the dose

level where at least two participants develop toxicities consistent with a DLT definition. In this situation, the dose level immediately below the MAD will be defined as the MTD. In the event that dose level 1 is found to be intolerable (with either 2/3 or $\geq 2/6$ patients experiencing a DLT), the trial will be discontinued. In the situation where none of the dose levels have ≥ 2 DLTs, the MTD will be the highest dose administered (i.e. dose level 3). The MTD will be defined in a minimum of six patients.

In the event that dose level 3 is found tolerable (with ≤ 1 of 6 participants experiencing DLT); subsequent higher dose levels may be explored following a full protocol amendment as long as the LY3022855 dose does not exceed the identified RP2D of LY3022855 single-agent therapy. Upon declaring the MTD, the Overall Principal Investigator will review safety data generated during the phase 1 portion of the trial to decide the RP2D of the combination. This review will include a review of the DLTs that occurred among the dose levels in conjunction with toxicities experienced among participants beyond the DLT time frame. Once the RP2D has been defined, the phase II portion of the trial will begin with enrollment of 25 patients with either BRAF V600E or V600K mutant melanoma. Patients enrolling into the phase II portion of the trial will be treated at the RP2D for the combination identified during the phase I portion of the study.

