Patients enrolled to the phase I dose escalation portion of the trial will be required to have received at least 75 percent of their doses of vemurafenib and cobimetinib, and must complete at least three of the four LY3022855 infusions during the first cycle to be considered evaluable for DLT purposes. Patients who do not meet these parameters during cycle 1 for reasons other than toxicity (for example, withdrawal of consent for participation on the trial, or rapid disease progression and subsequent removal from the trial) will be replaced.

Participants will be requested to maintain a study medication diary that will indicate each dose of oral medication taken to illustrate treatment compliance. The medication diary should be returned to appropriate research staff for review at the end of each treatment cycle.

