13.2 Sample Size, Accrual Rate and Study Duration

The planned sample size is between six and 18 patients in the phase I portion of the trial, and 25

patients in the phase II portion of the trial, for a total of 31 to 43 patients. The planned accrual rate is approximately 5 patients per quarter. Up to an additional one year of follow-up will be required for the last participant accrued to observe the patient's response and survival following therapy, for a total study length of about four years. Participants will be identified via targeted NextGen sequencing using the DFCI/BWH OncoPanel or another CLIA-certified method for genotyping.

Table 26: Accrual Targets					
Ethnic Category	Sex/Gender				
Zumie Cutegory	Females		Males		Total
Hispanic or Latino	0	+	1	=	1
Not Hispanic or Latino	15	+	27	=	42
Ethnic Category: Total of all subjects	15	+	28	=	43
Racial Category					
American Indian or Alaskan Native	0	+	1	=	1
Asian	0	+	0	=	0
Black or African American	0	+	0	=	0
Native Hawaiian or other Pacific Islander	0	+	0	=	0
White	15	+	27	=	42
Racial Category: Total of all subjects	15	+	28	=	43

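### The phase I minimum of six patients, and the total of 31 built on it, cannot occur under the plan's own 3+3 rules; the minimum is 9, or 34 if phase II opens

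*Combined protocol and SAP*

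**What the plan says.** - **Sample size.** Section 13 gives phase I a "minimum of six and a maximum of 18 patients to determine the MTD and RP2D". Section 13.2 repeats six to 18, adds 25 for phase II and concludes "for a total of 31 to 43 patients". Table 26 breaks the 43 down by sex, ethnicity and race.
- **Start and dose levels.** Section 5.1 opens with "Three patients will be enrolled to dose level 1". Table 10 lists three levels, and level 1 is the lowest.
- **Escalation (Table 11).** With no DLT in three patients, three enter at the next level. With one in three, at least three more enter at the same level. If none of these has a DLT, escalation continues. With two or more DLTs, escalation stops and the level below is filled to six if it holds only three.
- **MTD (section 5.1).** The MTD is the level just below one with at least two DLTs. If no level reaches two, "the MTD will be the highest dose administered (i.e. dose level 3"). In both cases, "The MTD will be defined in a minimum of six patients". Table 11 also requires at least six patients at the RP2D.
- **Level 1 not tolerated.** Sections 5.1 and 13.1 both discontinue the trial.
- **Replacement (section 5.1).** Patients who are not evaluable for DLT for reasons other than toxicity, such as withdrawal of consent or "rapid disease progression and subsequent removal from the trial) will be replaced".

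**The concern.** Six is the number of patients that the plan requires at one dose level, yet section 13 gives it as the size of the whole of phase I. Under a 3+3 scheme with three levels and nothing below the starting level, level 1 becomes the MTD only once a higher level has been tried and has failed. So six patients in all looked too few, and 31 looked like a trial in which phase II opens after a phase I that could not have named a dose.

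What is at stake is the accuracy of a core protocol figure that appears in two sections and contradicts the dose-escalation rules. Anyone planning on the lower end of the range would be planning for a trial that the rules do not allow.

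**Working it through.** **Check that the rule is read correctly.** Section 13.1 gives escalation probabilities of 91, 71, 49, 31 and 17% for true DLT rates p of 10, 20, 30, 40 and 50%. Escalating on 0/3, or on 1/3 followed by 0/3, has probability

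(1−p)³ + 3p(1−p)² × (1−p)³ = (1−p)³ + 3p(1−p)⁵

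| p | Computed | Section 13.1 |
|---|---|---|
| 0.1 | 0.906 | 91% |
| 0.2 | 0.709 | 71% |
| 0.3 | 0.494 | 49% |
| 0.4 | 0.309 | 31% |
| 0.5 | 0.172 | 17% |

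All five agree, so the rule used below is the plan's own: 1/6 leads upward and does not end phase I.

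**Reproduce the stated totals.**
- Upper: 3 levels × 6 = 18, and 18 + 25 = 43. Both reproduce.
- Lower: 6 + 25 = 31 is correct as addition. The question is whether six can occur.

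**Shortest path to each MTD.** The inputs are cohorts of three (Table 11), three levels (Table 10) and at least six patients at the MTD (section 5.1).
- MTD = level 1: level 1 has 0/3, level 2 has at least 2/3, and level 1 is filled to six. 6 + 3 = **9**.
- MTD = level 2: level 1 has 0/3, level 2 has 0/3, level 3 has at least 2/3, and level 2 is filled to six. 3 + 6 + 3 = **12**.
- MTD = level 3: levels 1 and 2 have 0/3, and level 3 is filled to six. 3 + 3 + 6 = **12**.

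**All paths.** Every sequence of cohorts under Table 11 was enumerated, including de-escalation and filling the MTD level to six.

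| Outcome | Possible phase I sizes (evaluable patients) |
|---|---|
| MTD = level 1 | 9, 12, 15, 18 |
| MTD = level 2 | 12, 15, 18 |
| MTD = level 3 | 12, 15, 18 |
| No MTD, trial discontinued | 3, 6, 9, 12, 15, 18 |

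Sizes 3 and 6 appear only in the last row. They arise when level 1 has at least two DLTs in its first three patients, or one in three followed by at least one more in the next three. Phase II then never opens. (Level 1 can also fail later, after de-escalation, which explains the larger sizes in that row.)

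**Totals when phase II opens.** Minimum 9 + 25 = **34**, against 31 stated. Maximum 18 + 25 = 43, as stated.

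**The case against.** **Six could be the smallest phase I of any kind.** It is not: that would be 3, when two of the first three patients have a DLT. Section 13 also ties six to determining the MTD and RP2D, and 13.2 adds the 25 phase II patients to it.

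**Nine is not absolute.** Table 11's stopping row requires two or more DLTs without saying out of how many. If the first two patients at level 2 both had DLTs and entry stopped there, 6 + 2 = 8 would suffice. This stands as an edge case. Table 11 enters cohorts of three, so 9 is the figure under the rules as written, and six is out of reach either way.

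**The dose levels might be cut short.** Section 5.1 caps LY3022855 at its single-agent recommended phase II flat dose, so in principle levels 2 and 3 might never open. But section 5.1 defines the MTD only as the level below a failed one or as level 3, and section 2.5.2 describes 100 mg weekly, the top level here, as tolerable so far in the single-agent study. Nothing in the plan presents six as the size for that case.

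**Nothing rests on the lower bound.** This stands, and it limits the weight of the point. Table 26 uses 43. Phase II power uses 25 patients and 12 events. The escalation rules and the six patients at the MTD are unchanged.

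**A reader might infer that the upper figures are wrong too**, because replacements are left out, and that an overrun would force an amendment or take places from phase II. The documents do not support this. The figures 18 and 43 are exact for DLT-evaluable patients, and section 5.1 already states the replacement rule, so section 13 only lacks a detail. The 25 is fixed separately, and section 13.3 keeps phase I patients out of the phase II evaluations. Table 26 is headed as targets, and no section says what follows if 43 is passed. The longest path is also uncommon: under assumed DLT rates (flat 10, 20, 30 or 40%, or rising 10/20/30%), all 18 evaluable patients are used in 4.3, 6.5, 4.6, 2.1 and 7.4% of trials respectively. What remains is that enrolment can exceed 18 on that path. The documents give no non-evaluable rate. At an assumed 5 to 20%, 18 evaluable patients need 18/0.95 to 18/0.80, about 19 to 23 enrolled.

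**Conclusion.** The point holds for the lower bounds. Six patients cannot determine the MTD under Table 11 and section 5.1, and a total of 31 cannot occur in a trial that opens phase II. The minimum is 9 in phase I and 34 in total, a difference of three patients in each. This rests only on the plan's own rules with full cohorts of three; no DLT rate or replacement rate is assumed.

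The six was perhaps carried over from the minimum required at the MTD level, but that is an inference.

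The severity is minor: a stated sample size is wrong as written, with no effect on the dose rules, the phase II size or power, or the escalation probabilities.

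**What to change.** - **Section 13:** give the phase I size as 9 to 18 DLT-evaluable patients to determine the MTD, and 3 or 6 if dose level 1 is not tolerated in its first three or six patients and the trial stops.
- **Section 13.2:** use the same phase I range, and give the total as 34 to 43 if phase II opens.
- **Optional:** add to both that patients replaced under section 5.1 come on top of these figures.

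Table 26 need not change. The cost is a few words in two sections; no dose, rule, analysis or target changes.
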